7.1.2. Analysis Methods for Albuterol Use

7.1.2.1. Pattern of Baseline Daily and Weekly Albuterol Use

Summary statistics including 95% CIs of the proportion of eMDPI time on study days when a patient took 0 to 4 inhalations a day (number of days a given patient took 0 to 4 inhalations a day divided by the total number of eMDPI study days for a given patient) will be summarized overall and by CAE status and by CAE severity. In addition, the proportion of patients exhibiting

weekly baseline albuterol use (Week 1, Week 2, ..., Week 12) will be summarized overall and by CAE status and by CAE severity.

Week 1 and Week 2 patient albuterol use patterns, “WK1:I#iD#dMT4Y/N” and “WK2:I#iD#dMT4Y/N” designation, will be summarized descriptively (counts and percent) overall and by CAE status and by CAE severity.

7.1.2.2. Total Number of Inhalations in the Days Preceding the Peak of a CAE

For patients who experienced a CAE, summary descriptive statistics of the total number of inhalations taken in 1 day (eg, the 24-hour period on the day prior to the date of the CAE symptom peak) and at 3, 5, 7, 10, 14, and 21 days preceding the date of the CAE symptom peak will be presented overall and by moderate CAEs and severe CAEs.

In this analysis, among patients experiencing more than 1 CAE, the subsequent CAEs can be considered a separate CAE distinct from the first (preceding) CAE provided the patient exhibited at least 1 day of baseline albuterol use after the first (preceding) CAE’s date of symptom peak and prior to the subsequent CAE’s date of symptom peak. For patients who experience multiple CAEs (eg, 3), for a given number of days preceding a CAE (eg, 21 days), if the (eg, third) CAE overlaps with the time period of the preceding (eg, second) CAE, the CAE (eg, third CAE) should not be included in the analysis.

Mean and 95% CI of the total number of inhalations per day for each eMDPI study day will be summarized graphically. The number of patients contributing to the summary statistic at study at Day 7, 14, 21, 28, 35, 42, 49, 56, 63, 70, 77, and 84 will also be presented. Three line graphs will be presented in 1 figure: “Overall” and by “CAE Status” (Yes, No). Three line graphs will be presented in a second figure; “CAE Status No”, “CAE Status Yes: Severe” and “CAE Status Yes: Moderate”.

A figure summarizing the mean (+/- minimum and maximum) of the total number of inhalations per day for each patient experiencing multiple CAEs will be presented for the time period of 21 days prior to the date of symptom peak of the first CAE to 21 days after the date of symptom peak of the last CAE. The x-axis will be labeled -21, -20, ..., -1, 0, 1, 2, ..., D , where day 0 is the date of symptom peak of the first CAE and D is the study day number 21 days after the date of the symptom peak of the last CAE.

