2.3. Sample Size and Power Considerations

Assuming an expected dropout rate of 10%, it is recommended that 400 patients be enrolled so that 360 evaluable patients complete the study. The rationale is based on a review of the relevant literature, as follows.

Based on previous studies of a poorly-controlled exacerbating asthma cohort ([Bateman et al 2015](#), [Ko et al 2012](#), [McCarren et al 1998](#), [Quezada et al 2016](#)), it is expected that between 20% and 25% of subjects at risk in this patient population will experience a CAE (event) over 3 months, resulting in 72 to 90 expected CAE events in this study. In addition, it is expected that approximately 6.7% and 15% ([Bousquet et al 2007](#), [Ko et al 2012](#), [Kuna et al 2007](#), and [Rabe et al 2006](#)) of subjects at risk in this patient population will experience moderate and severe events, respectively, resulting in approximately 78 events (24 moderate events and 54 severe events) in this study.

This sample size (n=400 patients; 72 to 90 CAE events) is considered adequate for fulfillment of the study objectives using univariate and multivariate analyses to evaluate the relationship of the pattern of albuterol use, inspiratory flow, SDI, and TDS data associated with the subsequent development of a moderate CAE or severe CAE. Per the study by Patel ([Patel et al 2013](#)), a statistically significant relationship was established between prior mean daily SABA usage at baseline and subsequent CAE, studying 45 exacerbations ($p < 0.006$).

In the present study, approximately 72 to 90 CAE events are desired for this trial because the model's fitting of the current study involves the analysis of multiple predictors as described in more detail below.

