7.1.1. Albuterol Use Definition

Baseline albuterol use is defined as no more than 4 inhalations (eg, 0 to 4 inhalations) per day of use regardless of the number of days albuterol is used in a 7-day period.

Daily baseline albuterol use is defined as no more than 4 inhalations (eg, 0 to 4 inhalations) per day.

Week 1 Patient Albuterol Use: Week 1 patient albuterol use is each patient's total number of albuterol inhalations taken and the number of days used during the first week (study day 1 through study day 7) of study participation with an indicator of whether or not any daily usage of albuterol exceeded 4 inhalations. It is presented as WK1:I#iD#dMT4Y/N, where "i" is the number of albuterol inhalations and "d" is the number of days used in the first 7 days of the study, and "MT4Y/N" is an indicator of whether or not any of the days albuterol was used exceeded 4 inhalations. For example, "I28D7MT4N" indicates a total of 28 inhalations were taken, albuterol use was used each day and none of the daily number of inhalations exceeded 4 (No More Than 4 inhalations per day Yes/ No).

Week 2 Patient Albuterol Use: Week 2 patient albuterol use is each patient's total number of albuterol inhalations taken and the number days used during the second week (study day 8 through study day 14) of study participation with an indicator of whether or not any daily usage of albuterol exceeded 4 inhalations. It is presented as "WK2:I#iD#dMT4Y/N", where "i" is the number of albuterol inhalations and "d" is the number of days used in the second week of study.

Albuterol use will be examined by the following 3 parameters; (i) total number of inhalations in the days preceding the peak of a CAE, (ii) number of days prior to the peak of a CAE when albuterol use increased, and (iii) number of albuterol uses in the day preceding a CAE.

The maximum number of inhalations taken within a 24-hour period by each patient: The date and time stamp of the inhalations are taken into consideration when determining the maximum number of inhalations taken within a 24-hour period by each patient. For patients who experienced a CAE, the maximum number of inhalations taken within a 24-hour period is determined among the days prior to the date of the symptom peak of the exacerbation.

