7.2.2.2. Actual and Change from Baseline in Week *Y* Inhalational Flow Values

Summary descriptive statistics of the actual inhalational flow values and change from baseline in MIF, inhalational volume, inhalation duration, and time to MIF for each study week (1 through 12) will be presented overall, and by CAE status and by CAE severity.

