7.4.2.2. Actual and Change from Baseline in Week Y Sleep Disruption Indices

Summary descriptive statistics of the absolute Week Y nighttime average sleep latency time, longest nighttime wake episode, total time awake at night, and SDI composite score and change from baseline in these four sleep disruption indices for each study week (1 through 12) will be presented overall, and by CAE status and by CAE severity.

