7.5. Clinical Asthma Exacerbation

7.5.1. Clinical Asthma Exacerbation Definition

A CAE is the primary outcome measure of this study. In this study, a CAE is an occurrence of either a "severe CAE" or a "moderate CAE." defined as the following:

- A severe CAE is defined as a CAE that involves worsening asthma such that
 - the treating physician elects to administer prednisone (or equivalent glucocorticoid treatment) at least 10 mg prednisone equivalent above baseline (Table 2), for at least 3 daysAND
 - an unscheduled provider visit such as an office visit, urgent care visit, emergency care visit, or hospitalization
- A moderate CAE is defined as a CAE that involves worsening asthma such that
 - the treating physician elects to administer prednisone (or equivalent glucocorticoid treatment) at least 10 mg prednisone equivalent above baseline (Table 2), for at least 3 days

OR

- an unscheduled provider visit such as an office visit, urgent care visit, emergency care visit, or hospitalization associated with an increase in asthma therapy that does not qualify for “severe CAE” as defined above

Table 2: Systemic Glucocorticoid Treatment Equivalent to 10 mg of Prednisone

Glucocorticoid Treatment	Dose (mg) Equivalent to 10 mg of Prednisone	Comment
Cortisone	50	Includes parenteral
Hydrocortisone	40	Cortisol
Prednisolone	10	-
Methylprednisolone	8	Medrol: includes parenteral SOLU-MEDROL®
Triamcinolone	8	-
Betamethasone	0.4	-
Dexamethasone	0.4	Oral or parenteral DECADRON®

The designation of a CAE as moderate or severe is denoted by the response to the CRF question “Severity” on the Clinical Asthma Exacerbation CRF page regardless of whether the following CRF questions are answered in the negative or missing:

- “The treating physician elects to administer prednisone (or equivalent glucocorticoid treatment) at least 10 mg prednisone equivalent above baseline, for at least 3 days”
- An unscheduled provider visit such as an office visit, urgent care visit, emergency care visit, or hospitalization

A patient may experience more than 1 CAE during the study period.

Clinical Asthma Exacerbation Status: Clinical asthma exacerbation status is an indicator of whether or not a patient experienced a CAE during study follow-up (Yes, No).

Clinical Asthma Exacerbation Rate: The percentage of patients who experience at least 1 moderate or severe CAE at the end of study follow-up.

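### Several descriptive comparisons by CAE status use the whole follow-up, so days during and after the exacerbation can create a Yes/No difference, in either direction, with no difference before the CAE.

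*SAP*

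**What the plan says.** SAP 7.5.1 defines CAE status as an "indicator of whether or not a patient experienced a CAE during study follow-up (Yes, No"), so one CAE at any time places the patient in CAE: Yes for every day. Follow-up does not stop there: 7.5.1 allows for more than one CAE per patient and defines a recurrent rate.

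These by-status outputs have no cut at the CAE:

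- **7.1.2.1.** The number of 0-to-4-inhalation days is "divided by the total number of eMDPI study days for a given patient) will be summarized overall and by CAE status". By 4.4, eMDPI time runs from first dispensing to last device return. The proportion of patients with baseline use is also given for each of Weeks 1 to 12.
- **7.1.2.2, figures.** "Mean and 95% CI of the total number of inhalations per day for each eMDPI study day will be summarized graphically", with separate lines by CAE status and severity.
- **7.2.2.2 and 7.3.2.2.** Flow values and steps are tabulated "for each study week (1 through 12) will be presented overall, and by CAE status and by CAE severity".
- **7.4.2.2.** Sleep is treated likewise, including "change from baseline in these four sleep disruption indices for each study week (1 through 12").
- **7.2.2.1 and 7.4.2.1.** The maximum changes from baseline in flow and sleep are summarized by status with no limit on which days count.

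Two parallel measures do have a cut. For CAE patients, the maximum number of inhalations in 24 hours (7.1.1) "is determined among the days prior to the date of the symptom peak of the exacerbation", and the maximum change in steps (7.3.2.1) uses only days before the exacerbation.

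**The concern.** The study objective (SAP 1.1) is the pattern of albuterol use before a CAE. In the listed outputs, the CAE: Yes group mixes run-in days with days when the patient is already exacerbating or recovering. Rescue use, inspiratory flow, steps and sleep may all change then because of the CAE and its treatment. A gap between the Yes and No lines may therefore be a consequence of the exacerbation and not a forerunner of it.

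These contrasts matter because the analyses that look directly at the run-in to a CAE (7.1.2.3, 7.5.2.1) use only patients who had one. They cannot show whether a pattern separates patients who exacerbate from those who do not. The protocol's logistic models, which could, have been moved out of the SAP to a separate report (7.5.3, 20.4). The 0-to-4-day share and the daily curves carry 95% CIs, which invites an inferential reading, and no sensitivity analysis is planned (Section 8).

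**Working it through.** **Step 1. The plan's own figures.** SAP 2.3 says "it is recommended that 400 patients be enrolled so that 360 evaluable patients complete the study". With 10% dropout, 400 × 0.90 = 360. Expected events are 360 × 0.20 = 72 and 360 × 0.25 = 90. By severity, 360 × 0.067 = 24.1 and 360 × 0.15 = 54, about 78 in total. All reproduce. With one CAE per patient (an assumption), the groups are 78 CAE: Yes and 360 − 78 = 282 CAE: No. The documents give no figure for a Yes/No difference.

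**Step 2. Effect on mean daily use.** Assumptions not in the documents: equal usual use in both groups, one 14-day episode from onset, onset uniform over 84 study days, and use in the episode k times usual.

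- Mean episode days inside follow-up = 14 − (1 + 2 + … + 13)/84 = 14 − 91/84 = 12.92.
- Share of follow-up = 12.92/84 = 15.4%.
- Spurious relative excess in CAE: Yes = 15.4% × (k − 1).
- k = 2, 3, 4 gives 15%, 31%, 46%. The true pre-CAE difference is zero.

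**Step 3. Effect on the 0-to-4-day share.** This was simulated with 78 versus 282 patients. Patient means were gamma (mean 2 inhalations/day, shape 1) with Poisson daily counts, the same in both groups. Onset was uniform on days 15 to 84, and use was multiplied by k from onset for 7, 14 or 21 days. There were 600 runs per scenario.

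| Episode | k | Yes minus No, points | 95% CI excludes 0 |
|---|---|---|---|
| 7 days | 2 to 4 | −1.5 to −3.2 | 7% to 18% of runs |
| 14 days | 2 to 4 | −3.0 to −6.2 | 16% to 52% |
| 21 days | 2 to 4 | −4.3 to −9.3 | 24% to 85% |
| 7, 14, 21 days | 0.5 | +0.8, +1.6, +2.1 | 8.5%, 11.0%, 15.8% |
| none (1500 runs) | 1 | 0.0 | 5.0% |

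A hand check for 14 days: mean episode days = 14 − 91/70 = 12.7, or 12.7/84 = 15.1% of follow-up. A gamma-Poisson count with shape 1 and mean m exceeds 4 with probability (m/(1 + m))^5.

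- Usual use, m = 2: (2/3)^5 = 0.132.
- k = 2, m = 4: (4/5)^5 = 0.328, so 0.151 × (0.132 − 0.328) = −3.0 points.
- k = 4, m = 8: (8/9)^5 = 0.555, giving −6.4 points (simulated −6.2).
- k = 0.5, m = 1: (1/2)^5 = 0.031, giving +1.5 points (simulated +1.6).

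**Step 4. The same data cut at onset.** With CAE: Yes limited to pre-onset days, the difference is between −0.2 and +0.2 points in every scenario, and the CI excludes zero in about 5% to 7% of runs. The within-patient difference between the 7 days before onset and the 7 days before those stays within ±0.005 inhalations per day.

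**Step 5. A one-sided cut on a maximum.** Cutting only CAE: Yes patients at onset makes their mean maximum daily count 0.44 to 0.50 lower than CAE: No, because their window is shorter. Maxima therefore need a matched window.

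**The case against.** The strongest reply is that none of these outputs is a hypothesis test. The amendment history calls the study exploratory, and the SAP attaches no predictive claim to these tables. Protocol 3.3 aims at the natural history of CAE, and one figure in 7.1.2.2 deliberately runs to 21 days after the last symptom peak. This stands: it lowers the severity and justifies keeping a labelled whole-follow-up version. It does not make the unlabelled Yes/No contrasts interpretable as use before a CAE.

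A reader might infer four stronger things that the documents do not support:

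- **That the test of a pre-CAE rise is biased.** The run-in totals (7.1.2.2) and the t-test (7.1.2.3) stop at the symptom peak. The paired weeks (7.5.2.1) stop at symptom onset after 14 CAE-free days. The landmark analysis (7.5.2.2) looks forward from the use event, and 7.5.2.3 uses CAE-free days. None has this fault.
- **That every by-status summary is affected.** The maximum 24-hour inhalations and the maximum step change are cut before the peak or the exacerbation. The Week 1 and Week 2 patterns cover days 1 to 14 only, so they are affected only if a CAE falls in those days.
- **That the share of days over 12 inhalations is inflated in CAE: Yes.** SAP 7.1.2.4 gives that share only for patients without a CAE, so no such comparison is planned.
- **That the bias must raise apparent use.** Protocol 5.6 prohibits nebulized albuterol only outside a CAE, and a CAE may involve hospitalization, so eMDPI counts could fall.

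**Conclusion.** The point holds for the outputs listed above. As written, a Yes/No difference in them can arise with no difference before the CAE, and its direction is not known in advance. For a 14-day episode, the illustration gives a spurious 15% to 46% excess in mean daily use and a 0-to-4-day share 3.0 to 6.2 points lower at 2 to 4 times usual use, or 1.6 points higher if eMDPI use halves. The multipliers, episode lengths, use distribution and onset pattern are assumptions, so these are examples and not estimates. No size is offered for flow, steps or sleep, because the documents give nothing to base one on. That these outputs have no cut at the CAE rests on the SAP text alone. Severity is moderate: the outputs are descriptive, and the direct pre-CAE analyses are not affected.

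**What to change.** - **Study-day figures and weekly tables** (weekly proportions in 7.1.2.1; 7.1.2.2, 7.2.2.2, 7.3.2.2, 7.4.2.2): let CAE: Yes patients contribute only days, or whole weeks, before the symptom onset of their first CAE. Compare them on the same study days or weeks with CAE: No patients still on study. A comparator of everyone still CAE-free would not do, because it contains the CAE: Yes patients being compared.
- **Per-patient share (7.1.2.1) and maximum changes in flow and sleep (7.2.2.1, 7.4.2.1):** apply the same cut and give each CAE: No patient a matched window, for example one ending at an index day drawn from the observed CAE onset days.
- **Whole-follow-up versions:** keep any of these as a separate table or line, labelled as including CAE and post-CAE days.

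The onset date is already used in 7.5.2.1, so the change needs SAP wording, a date filter, an index-day rule and a few extra tables. Under 2.4.2, it should be approved before database lock. The price is fewer CAE: Yes patients in later weeks. In these outputs, run-ins to recurrent CAEs also drop out, but 7.1.2.2 and 7.5.2.1 still cover those under their own conditions.

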7.1.2.3. Hypothesis: Albuterol Use Will Increase Several Days Prior to a CAE

The hypothesis under consideration is that albuterol use will increase several days prior to a CAE. Several days will be defined as 7 days prior to the date of the CAE symptom peak for this analysis.

For each subject that experiences at least 1 CAE, Y_1, \dots, Y_7 will represent the number of puffs of albuterol during the 7 days preceding the date of the CAE symptom peak and let Y_8, \dots, Y_{14} will represent the number of puffs taken each day during day 8 through 14 preceding the date of the CAE symptom peak. Under the hypothesis of no increased albuterol use preceding an exacerbation (ie, null hypothesis) assume for subject “xxx” that $Y_i \stackrel{iid}{\sim} Poisson(\lambda_{xxx})$ for all subjects i . Alternatively, if albuterol use does increase prior to an exacerbation, then

$Y_i \stackrel{iid}{\sim} \text{Poisson}(\lambda_{xxx})$ during day 8 through 14 preceding the date of the CAE symptom peak and $Y_i \stackrel{iid}{\sim} \text{Poisson}(\lambda_{xxx} + \delta)$ for the immediate 7 days preceding the CAE(s). Also, for random subject effect, assume λ_{xxx} follows some distribution to account for subject to subject variability. Let d_{xxx} will equal to the mean number of puffs during the 7 days immediately preceding the date of the CAE symptom peak minus mean number of puffs during days 8 through 14 preceding the date of the CAE symptom peak. To assess if albuterol usage increases 7 days prior to a CAE, $H_0: \mu_D = 0$, $H_1: \mu_D > 0$ will be tested using a t-test at the 0.05 significance level.

7.1.2.4. Number of Days Prior to the Peak of a CAE When Albuterol Use Increased

Among patients who experienced a CAE, summary statistics of the number of days prior to the peak of a CAE when albuterol use increased will be presented overall and by moderate CAEs and severe CAEs for 3 thresholds defining an increase in albuterol use;

- (i) First occurrence of a single day's albuterol use exceeding 4 inhalations;
- (ii) First occurrence of a single day's albuterol use exceeding 12 inhalations;
- (iii) First occurrence of a single day's albuterol use exceeding 20 inhalations.

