7.5.2.1. Within Patient CAE Analyses

For each CAE event occurring at least 2 weeks after baseline, device-use measures (albuterol use, inhalational flow [MIF], inhalational volume, and time to MIF) will be summarized for each of 2 weeks of interest: first- 'CAE-adjacent week', the week immediately preceding the onset of CAE symptom (ie, day 1 through 7 preceding the date of the CAE symptom onset), and second – 'CAE-Prior Adjacent week', the week preceding that week (ie, during day 8 through 14 preceding the date of the CAE symptom onset). Summary measures of daily and or weekly use will be compared between the two weeks, as proposed below:

Albuterol use measures:

- total number of inhalations in that week
- the maximal daily number of inhalations in that week
- the mean number of daily inhalations (ie, total number of inhalations divided by number of days with number>0)
- occurrence of a single day's albuterol use exceeding 4 inhalations;
- occurrence of a single day's albuterol use exceeding 8 inhalations
- occurrence of a single day's albuterol use exceeding 12 inhalations
- number of days when albuterol use exceeding 4 inhalations;
- number of days when albuterol use exceeding 8 inhalations
- number of days when albuterol use exceeding 12 inhalations

To note, in this analysis, no inhalation in any day will be taken as a 0 count.

Inhalation flow values parameters:

- maximal daily MIF during the week
- minimal daily time to MIF within a week
- maximal total daily inhalational volume within a week,

To note, if no inhalation was taken at a specific day, flow value parameters will be missing and will not be imputed.

Analysis will be based on all patients CAEs for which there are 14 days (or more) prior to the CAE onset, where patient has been on study and CAE free.

Descriptive statistics of use measures in the 'CAE-adjacent week' and 'CAE-Prior Adjacent week' will be presented.

Continuous measures will be compared between the 2 weeks using paired t-test (and Wilcoxon Signed Ranks test) whereas binary patterns will be compared using Mc-Nemar test.

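### Albuterol look-back totals (SAP 7.1.2.2) and the 14-day comparison (SAP 7.1.2.3) set no minimum time on study, so early CAEs give truncated totals and an undefined or partly observed difference

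*SAP*

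**What the plan says.** **SAP 7.1.2.2.** The population is all patients with an event: "For patients who experienced a CAE, summary descriptive statistics of the total number of inhalations taken in 1 day", then "and at 3, 5, 7, 10, 14, and 21 days preceding the date of the CAE symptom peak". The only exclusion tied to the window concerns a later CAE whose window runs into the preceding CAE: "the CAE (eg, third CAE) should not be included in the analysis". A window that runs back past Day 1 is not mentioned.

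**SAP 7.1.2.3.** The population is again everyone with an event: "For each subject that experiences at least 1 CAE". The patient-level difference is the mean for the 7 days before the peak "minus mean number of puffs during days 8 through 14 preceding the date of the CAE symptom peak". The alternative is an increase only, and the difference "will be tested using a t-test at the 0.05 significance level". No minimum time on study is given.

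**SAP 7.5.2.1.** This makes nearly the same comparison (days 1 to 7 against days 8 to 14, counted back from symptom onset), but it is restricted: "For each CAE event occurring at least 2 weeks after baseline", and only where the patient has been on study and free of CAE for at least 14 days. It also scores a day without inhalation as zero, and limits that rule to its own analysis.

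**Related rules.** SAP 4.5 sets Day 1 at first dispensing. SAP 4.6 lists the imputation rules; none covers albuterol counts on days before dispensing. Protocol 9.3 uses observed data only unless the analysis plan says otherwise.

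**The concern.** A CAE that peaks on study day 10 has 9 earlier device days. It can add at most 9 days of use to a total labelled 14 or 21 days, and only 2 of the 7 days that 7.1.2.3 needs for its comparison week. Such events are to be expected: entry requires a severe CAE in the past 12 months and an ACQ-5 score of at least 1.5, and Protocol 4.2 does not bar a recent exacerbation.

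Inhalations in the days before the peak are the first albuterol parameter of interest named in Protocol 2.1. A total that mixes full and truncated windows understates that parameter, and the understatement grows with the window. In 7.1.2.3 the missing days always fall in the earlier week first, so how they are handled decides whether the difference is undefined, unbiased or pushed upwards.

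**Working it through.** **The plan's event numbers (SAP 2.3).** 400 × 0.90 = 360 evaluable; 360 × 20% = 72; 360 × 25% = 90; 360 × 6.7% = 24.1 and 360 × 15% = 54, about 78 in all. These reproduce. The plan gives no power calculation for the 7.1.2.3 test.

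**Assumptions.** Peak day P is uniform on 1 to 84 (12 weeks), with one CAE per patient and constant daily use. A peak on day P has P − 1 earlier device days. The totals are read as cumulative over the window, which the section title and the overlap rule support.

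**Share of CAEs without a full L-day window** = L/84.

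**Shortfall in the mean total** = Σ(L − k)/(84L) for k = 0 to L − 1, which equals (L + 1)/168.

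| L (days) | Share short | Of 78 CAEs | Shortfall in mean total |
|---|---|---|---|
| 7 | 7/84 = 8.3% | 6.5 | 8/168 = 4.8% |
| 14 | 14/84 = 16.7% | 13 | 15/168 = 8.9% |
| 21 | 21/84 = 25% | 19.5 | 22/168 = 13.1% |

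If the hazard is doubled in the first 28 days (total weight 2 × 28 + 56 = 112), the shares are 14/112 = 12.5%, 28/112 = 25% and 42/112 = 37.5%. The shortfalls are 8/112 = 7.1%, 15/112 = 13.4% and 22/112 = 19.6%.

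**The 7.1.2.3 comparison week.** The day 8 days before the peak is study day P − 8, so peaks on days 1 to 8 have no day in the comparison week: 8/84 = 9.5%. Peaks on days 9 to 14 have part of it: 6/84 = 7.1%. Together these make 14/84 = 16.7%.

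**Effect on the t-test under the SAP null.** With absent days left out and means taken over observed days, the expected difference is 0 wherever it can be computed. With absent days entered as 0 (the same as a fixed divisor of 7), write k = P − 1. The shift is the mean of [min(7, k) − min(max(k − 7, 0), 7)]/7 in units of daily use. The numerators sum to 28 for k = 0 to 7 and to 21 for k = 8 to 14, so the shift is (28 + 21)/(7 × 84) = 0.083. At 5.5 actuations per day, the mean of the exacerbation group in the cohort cited in Protocol 3.3, that is +0.46 per day.

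Simulated one-sided type I error at nominal 0.05, 78 CAEs, flat timing, 4,000 to 6,000 runs per setting:

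| Daily use under the null | Absent days = 0 | Observed days only | Full 14 days required |
|---|---|---|---|
| Mean 5.5, SD 9.7 between patients, Poisson days | 0.44 | 0.05 | 0.05 |
| Mean 1.83, SD 3.3, Poisson days | 0.32 | 0.05 | 0.05 |
| Mean 5.5, SD 9.7, strong day-to-day overdispersion (day-level gamma shape 1) | 0.18 | 0.05 | 0.05 |
| Mean 6, SD 4.2 (gamma shape 2), Poisson days | 0.72 | 0.05 | 0.04 |

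The means and SDs in the first two rows are the cited cohort's figures, taking the ± values as SDs. Outside these settings the zero-fill figure goes down to about 0.12 with still heavier day-to-day variation (day-level gamma shape 0.5) and up to 0.78 if all patients use 5.5 per day.

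**The case against.** A reader might infer that the test in 7.1.2.3 is biased towards finding a rise. The documents do not support that as it stands. The bias needs pre-dispensing days to be scored as zero, and no text says so. Protocol 9.3 points to observed data only, SAP 4.6 has no such imputation rule, and the zero rule in 7.5.2.1 covers that analysis alone. On the favoured reading, type I error stays near 5%. What stands is that 7.1.2.3 states no handling at all, and that the only written convention for days without a count is zero, in a sister section where a full look-back makes it harmless.

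A reader might also take 7.1.2.3 to be the only formal test of the hypothesis. It is not. SAP 7.5.2.1 plans paired t-tests, signed-rank and McNemar tests on almost the same contrast, already restricted to full look-backs.

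The study is exploratory, 7.1.2.2 is descriptive, and no decision rule depends on it. That limits the consequence but does not remove the understatement. A sum over fewer days is too small whether the absent days are omitted or set to zero.

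Finally, dropping early CAEs has a price. Protocol 16.2, in explaining why the exclusion for a recent exacerbation was removed, says that risk is highest in the 30 days after an exacerbation and that albuterol use in these patients is of great interest.

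**Conclusion.** The concern holds for the totals and, in a conditional form, for the test.

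- **Totals (7.1.2.2).** Under flat timing and constant use, 8%, 17% and 25% of CAEs are truncated at 7, 14 and 21 days, and mean totals are low by about 5%, 9% and 13%. Early clustering makes this worse. If use rises towards the peak, as the study hypothesises, the missing days are the lower-use ones and the percentage shortfall is smaller. The direction is the same in every case.
- **Test (7.1.2.3).** About 10% of CAEs have no comparison week and a further 7% have an incomplete one, with no rule for either. If absent days are left out, there is no bias. If they were entered as zero, the null difference would be about +8% of daily use and one-sided type I error roughly 0.2 to 0.7, depending on assumed use and day-to-day variation.

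CAE timing, the spread of use and one CAE per patient are assumptions, since the documents give none of these for this study.

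**What to change.** 1. State in SAP 4.6 that days before first dispensing are missing, not zero.
2. In 7.1.2.2, report inhalations per observed day. Alternatively, for each L-day total include only CAEs with at least L prior study days. The second option uses a different set of CAEs at each L, so the windows would still not be comparable with one another.
3. In 7.1.2.3, apply the 7.5.2.1 condition of 14 CAE-free days on study, counted back from the date that anchors the analysis.
4. Report the number of CAEs in each window, and the observed days where windows may be short.

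This is SAP wording with no new data. Requiring full windows costs, under flat timing, about 17% of CAEs in the 14-day test (78 − 13 = 65 remain) and 25% at 21 days (78 − 19.5 = 58.5 remain). With the hazard doubled in the first 28 days the losses are 25% and 37.5%. All the CAEs lost are early ones. Per-observed-day reporting avoids most of this loss in the totals; only a peak on Day 1 itself (1/84 = 1.2%) has no prior day.
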